5.3 Exclusion criteria

Subjects who fulfil any of the following criteria will be ineligible to participate in the trial:

- 1. In the opinion of the investigator, the subject is unlikely to comply with the clinical trial protocol.
- 2. Has a functioning kidney transplant or is scheduled to receive a kidney transplant during the trial (Note: subject can be on waiting list for kidney transplant)
- 3. Subjects who receive peritoneal dialysis
- 4. In the opinion of the investigator has pruritus attributed to a cause other than CKD or its complications, including but not limited to dermatological disease (e.g., atopic dermatitis, psoriasis) or liver disease (cholestatic pruritus)
- 5. Has localized itch restricted to the palms of the hands
- 6. Only has pruritus during haemodialysis sessions
- 7. Has concurrent skin conditions (including but not limited to pruritic dermatoses, active skin infections, ulcerations) that may limit or prevent application of MC2-25 cream or MC2-25 vehicle or that may interfere with evaluation of the effects of MC2-25 cream or MC2-25 vehicle on the skin at the Screening or Baseline visits
- 8. Subjects who will have skin biopsies performed must not have any known hypersensitivity to the local anaesthetic or diagnosed bleeding disorders. Note: subjects with suspected uremic platelet dysfunction, without other bleeding diatheses, can be enrolled if the investigator agrees.

- 9. Known history of allergic reaction to any ingredients in MC2-25 cream or MC2-25 vehicle (see Section 6.1)
- 10. Has a concurrent or recent (within 12 months prior to screening) medical condition that, in the opinion of the investigator, could pose undue risk to the subject, impede completion of the trial procedures, or would compromise the validity of the trial measurements, including, but not limited to:
 - a. known or suspected abuser of alcohol, drugs, or narcotic substances
 - b. severe physical, mental, or cognitive disorder other than CKD
 - c. malignancy
 - d. failure to comply with local COVID-19 regulations on vaccination or testing (due to risk of transmitting the disease to other trial participants or trial staff).
- 11. Has an uncontrolled Human Immunodeficiency Virus (HIV) or a known active generalized infection (bacterial, viral, or fungal) that, in the opinion of the investigator, may interfere with the assessment of safety or efficacy in this trial
- 12. Is pregnant, breast feeding, or planning a pregnancy
- 13. Start of a new or change to existing systemic treatment for CKD-aP, including but not limited to antihistamines, corticosteroids, opioids, GABA analogues, or kappa opioid receptor agonists within 21 days prior to the Baseline visit
- 14. Use of emollients on CKD-aP areas within 10 days prior to the Baseline visit
- 15. Use of any topical treatment on CKD-aP areas, including but not limited to antihistamines, or corticosteroids within 21 days prior to the Baseline visit (Note: standard topical treatments used on or around a haemodialysis access site are allowed, e.g., local anaesthetics, sterilants)
- 16. Use of any light therapy for CKD-aP, including but not limited to UV-B within 35 days prior to the Baseline visit
- 17. Start of a new or change of existing non-biologic systemic immunosuppressive treatment, including but not limited to corticosteroids, cyclosporin, and tacrolimus within 21 days prior to the Baseline visit
- 18. Start of a new or change of existing biologic systemic treatment, including but not limited to etanercept, adalimumab, alefacept, infliximab, and ustekinumab within 3 months or 5 half-lives (whichever is longer) prior to the Baseline visit
- 19. Subjects who consent to having skin biopsies performed who are using anticoagulation treatment and are judged by the investigator to have an unacceptable risk of excessive bleeding in association with the skin biopsy

- 20. Subjects not currently on dialysis but who are likely to initiate routine dialysis during participation in the trial
- 21. Received another investigational drug within 30 days or 5 half-lives (whichever is longer) prior to screening or is planning to participate in another clinical trial while enrolled in this trial
- 22. Previously randomized in this trial

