6.7.2 Prohibited therapies from baseline to the end of the treatment period

Use of any therapy that would exclude the subject from participation in the trial (as specified in Section 5.3) is also prohibited during the treatment period, which includes therapies in the following categories:

- Start of new or change of existing systemic treatment for CKD-aP, including but not limited to antihistamines, corticosteroids, opioids, GABA analogues, or kappa opioid receptor agonists (but stable systemic CKD-aP treatment can be continued).
- Any topical treatment on CKD-aP areas, including but not limited to emollients, antihistamines, and corticosteroids

- Therapeutic anticoagulation treatment for subjects who have skin biopsies performed (heparin administered in association with dialysis is allowed but in such cases skin biopsies must not be performed on a dialysis day)
- Any light therapy for CKD-aP, including but not limited to UV-B
- Start of new or change of existing non-biologic systemic immunosuppressive treatment, including but not limited to corticosteroids, cyclosporin and tacrolimus
- Start of new or change of existing biologic systemic treatment, including but not limited to etanercept, adalimumab, alefacept, infliximab, and ustekinumab

If a prohibited therapy is used during the trial, treatment with the IMP shall not automatically be discontinued. After consultation with the sponsor's or designee's Medical Monitor, the investigator shall use his/her judgement to decide if (in the following prioritized order) 1) The prohibited therapy can safely be stopped; 2) the prohibited therapy cannot safely be stopped but the IMP treatment can safely continue alongside the prohibited therapy; or 3) the prohibited therapy cannot safely be stopped and the IMP treatment cannot safely continue alongside the prohibited therapy. The event must be reported as a protocol deviation.

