8.3 Analysis populations

The analysis populations are defined as follows:

Screened set (SS): all subjects who sign the informed consent form.

Safety analysis set (SAS): all subjects who are randomized and dispensed the trial medication at Randomisation/Day 0, excluding subjects to whom trial medication is not dispensed or who return all of the trial medication unused. Subjects will be analysed according to the actual treatment.

Full analysis set (FAS): all subjects who are randomized. Subjects will be analysed according to the randomized treatment.

Modified full analysis set (MFAS): all subjects who are randomized and returned for at least one post-baseline scheduled visit with data on WI-NRS. Subjects will be analysed according to the randomized treatment.

Per-protocol set (PPS): a subset of the MFAS subjects who completed the trial with WI-NRS data for Week 12 and are deemed to have no important protocol deviations that could interfere with the objectives of this trial. Important deviations of eligibility criteria and other deviations from the protocol will be assessed. Important deviations from the protocol may lead to exclusion of a subject or data points from the PPS, which could have interfered with the administration of the treatment or the evaluation of treatment effect. All such decisions will be identified and documented before the final trial database is unblinded. Important protocol deviations may include, but are not limited to, medication non-compliance, missing consecutive application days, and intake of prohibited concomitant therapies, which may have an impact on the primary endpoint.

The SAS will be used for all safety analyses. FAS, MFAS, and PPS will be used for efficacy analyses.

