For each copy of the imputed datasets, both the primary and secondary endpoints involving the same endpoint variable will be analyzed in the same way as described in the primary and secondary analyses in Sections 5.5.1 and 5.5.2, respectively. Results from the copies of the imputed datasets will be synthesized using SAS[®] Proc MIANALYZE.

Using the FAS for the primary endpoint analyses, a sensitivity analysis will be performed using last observation carried forward (LOCF; treatment policy). If a subject is given prohibited therapy, all missing data and data for visits after the start of prohibited therapy will use the MI approach described above in another analysis (hypothetical strategy).

If deaths occur, further estimands may be defined following a composite endpoint strategy.

There will be no imputation of missing data for the PPS which will use the data as observed following a treatment policy strategy. There will be no imputation of missing data for safety endpoints.

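### Criterion 19 admits some anticoagulated biopsy subjects whom Protocol 6.7.2 then places in deviation, and the SAP's hypothetical-strategy trigger would literally replace their itch scores

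*Protocol*

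**What the plan says.** Protocol 5.3, criterion 19, concerns subjects who consent to skin biopsy. It excludes those "using anticoagulation treatment and are judged by the investigator to have an unacceptable risk of excessive bleeding in association with the skin biopsy". Both conditions must hold: anticoagulation, and an adverse judgement of bleeding risk.

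Protocol 6.7.2 governs the period from Baseline to the end of treatment. It opens by presenting its list as the eligibility exclusions carried forward: "Use of any therapy that would exclude the subject from participation in the trial (as specified in Section 5.3) is also prohibited during the treatment". One bullet on that list is "Therapeutic anticoagulation treatment for subjects who have skin biopsies performed". The only exemption is for dialysis: "heparin administered in association with dialysis is allowed but in such cases skin biopsies must not be performed on a dialysis day". When a prohibited therapy is used, the site consults the Medical Monitor and works through three options in order of priority, of which the first is "1) The prohibited therapy can safely be stopped". The event must be reported as a protocol deviation.

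Biopsies are optional and limited to selected sites (Protocol Table 3, footnote 15). They are taken at Baseline and at Week 12 or Early Termination (Protocol 7.11.1).

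For the hypothetical strategy, Protocol 8.8.1 imputes missing data and all data after the start of rescue medication. SAP 5.2.1 has a different trigger: "all missing data and data for visits after the start of prohibited therapy will use the MI approach". SAP 5.2.3 repeats that trigger and says the affected WI-NRS values are set to missing before imputation.

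**The concern.** Two passages answer the same question differently. The question is whether a subject on a therapeutic anticoagulant may be in the biopsy subset. Criterion 19 leaves it to the investigator's view of bleeding risk. Section 6.7.2 answers no for every biopsied subject, while claiming to restate Section 5.3. A site that follows the eligibility section can enrol and biopsy a subject at Baseline and find that subject on a prohibited therapy the same day. These are conflicting instructions about an anticoagulant around an invasive procedure, in a trial with two planned biopsies per consenting subject.

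There is a smaller consequence for the analysis. The SAP ties its hypothetical strategy to the label of prohibited therapy, not to an effect on itch. The anticoagulation bullet exists for biopsy safety, and nowhere do the documents describe an anticoagulant as affecting itch. If the trigger is applied as written, observed itch scores are replaced by imputed ones for a reason unrelated to what that analysis is meant to estimate.

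**Working it through.** No sample-size or power figure in the plan is in dispute. The check sets the passages side by side and ends with a count of visits.

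1. **Eligibility.** Take a subject who consents to biopsy, takes a therapeutic anticoagulant unrelated to dialysis, and is judged at acceptable bleeding risk. The first condition of criterion 19 is met and the second is not, so the subject is not excluded.

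2. **From Baseline.** The 6.7.2 bullet applies to subjects who have biopsies performed. It has no exception for acceptable risk. Once biopsied, the subject is on a prohibited therapy and a deviation report is required.

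3. **The stated source.** The opening sentence of 6.7.2 prohibits therapies that would exclude a subject under Section 5.3. By step 1, Section 5.3 does not exclude this subject. The bullet therefore goes further than the sentence that introduces it.

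4. **Who is caught.** All of these must hold: consent to biopsy at a selected site; a biopsy actually performed; anticoagulation that is therapeutic and not dialysis heparin; and a judgement of acceptable risk. The heparin exemption does not empty this group. Strata B and C (Protocol 6.6.1) are not on dialysis and must make up at least 20% + 20% = 40% of subjects. The documents give neither the size of the biopsy subset nor the frequency of anticoagulant use.

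5. **Effect by analysis of the primary endpoint.**
   - FAS with multiple imputation (primary): treatment policy regardless of intercurrent events (Protocol 8.8.1; SAP 5.2.1). No values lost.
   - FAS with LOCF: treatment policy. No values lost.
   - MFAS with multiple imputation: treatment policy. No values lost.
   - FAS, hypothetical strategy: data after the start of a prohibited therapy are set to missing and imputed (SAP 5.2.1 and 5.2.3). Affected.

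6. **Visits affected in that one analysis.** Post-baseline weekly means are derived at Weeks 1, 4, 8 and 12, which is four per subject. The anticoagulant began before Baseline and the prohibition applies from Baseline. Whichever date counts as the start, all four visits come later, so 4 of 4 weekly means are replaced for such a subject.

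7. **Whether the SAP explains the wider trigger.** SAP Section 1 says that differences from the protocol's methods will be explained in the SAP. The table in SAP 6.2 has two entries: the added 70% threshold for complete response, and the deleted punch-biopsy biomarker analysis. The move from rescue medication to prohibited therapy is not among them.

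**The case against.** The best case for leaving the text alone has three parts. First, the conflict is narrow. Subjects on dialysis heparin, or on anticoagulation that is not therapeutic, can satisfy both passages, and an eligible subject who is never biopsied breaches nothing. Second, 6.7.2 does not leave the site without judgement. It requires consultation, asks whether the therapy can safely be stopped, and as its second option lets the therapy continue alongside the IMP. Third, SAP 5.2.1 speaks of a subject being given prohibited therapy. That can be read as something newly started, so a drug already in use before the trial might not trigger it.

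The first part stands and sets the scope. The second does not remove the conflict, because that pathway opens only after the prohibition has been breached and the deviation report is still required. The third shows that the SAP is ambiguous, which is itself a reason to reword it.

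Some stronger readings are tempting, and the documents do not support them.

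- A reader might infer that these subjects' itch data are discarded from the trial. They stay in the primary, LOCF and MFAS analyses.
- A reader might infer that the subjects drop out of the PPS. Protocol 8.3 limits its example to "intake of prohibited concomitant therapies, which may have an impact on the primary endpoint", exclusions are decided before unblinding, and SAP 5.2.1 and 5.2.3 contain no PPS exclusion for prohibited therapy.
- A reader might see a further conflict in the absence of anticoagulants from Protocol Table 2. That table covers criteria 13 to 18, each of which has a pre-baseline period. Criterion 19 has none, so its absence is expected.
- A reader might want a count of affected subjects. Any count would rest on guesses about biopsy uptake and anticoagulant use.

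**Conclusion.** The contradiction between criterion 19 and the anticoagulation bullet of 6.7.2 is real as written. An eligible subject on therapeutic, non-dialysis anticoagulation is in reportable deviation once biopsied. The number of such subjects is unknown, and the issue is confined to the optional biopsy subset at selected sites.

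The loss from the primary, LOCF and MFAS analyses is zero. In the hypothetical-strategy sensitivity analysis, a literal reading replaces all four post-baseline weekly means of each affected subject. That rests on two assumptions: an anticoagulant already in use counts as a prohibited therapy that has been given, and no unwritten limit to itch-active therapies is applied. The trial's main conclusion is not at risk. The case for acting is that the site instructions conflict around an invasive procedure, and that the SAP has an unexplained, over-broad trigger.

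**What to change.** 1. **Protocol.** Reconcile criterion 19 with the anticoagulation bullet of 6.7.2 so that a single rule decides whether an anticoagulated subject may be in the biopsy subset, and apply it at both biopsy time points. Which rule to adopt is for the sponsor to decide.

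2. **SAP.** In 5.2.1 and 5.2.3, limit the hypothetical-strategy trigger to prohibited therapies that can affect itch, so that the anticoagulation bullet does not activate it. Then either align the wording with Protocol 8.8.1 or list the change of trigger, with its reason, in SAP 6.2.

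The cost is a wording change in the protocol, handled as an amendment under Protocol 9.1 unless it counts as administrative, and a sentence or two in the SAP before database lock. No procedures, visits or subjects are added.

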5.4 Withdrawal from trial and discontinuation of treatment

In accordance with legal requirements and International Council for Harmonisation (ICH) – Good Clinical Practice (GCP) guidelines, every subject has the right to refuse further participation in this trial (withdrawal from trial) or refuse further treatment (discontinuation of treatment) at any time and without providing reasons. A subject's refusal should be effectuated immediately upon his/her request.

In addition, a subject may be withdrawn from the trial or be discontinued from treatment at any time at the discretion of the investigator.

Reasons for withdrawal from trial or discontinuation of treatment include (but are not necessarily limited to) progressive disease, AE, pregnancy, death, protocol violation, and lost to follow-up. If the IMP application is discontinued regardless of the reason for discontinuation, the subject should be encouraged to continue in the trial.

The reasons for trial withdrawal or treatment discontinuation are to be fully documented on the electronic case report form (eCRF) and an EoT visit should be completed as soon as possible to the extent possible. Subjects who withdraw from trial before randomization will be considered screen failures. In case of treatment discontinuation, the subject should be encouraged to attend remaining trial visits in line with the schedule of assessments (SoA). If a subject is withdrawn from the trial due to an AE or treatment is discontinued due to an AE, the AE must be followed up as outlined in Section 7.12.2.

If subjects are diagnosed with or have symptoms suggestive of COVID-19 they may not be allowed to attend trial visits until local regulations allow it. Subjects who are diagnosed with COVID-19 after randomization may subsequently be asked to complete trial visits (to the extent possible) via phone until applicable negative test results can be provided (if necessary, additional trial supplies may be shipped to the subject) or be withdrawn from the trial at the discretion of the investigator.

5.5 Replacement policy

Subjects who discontinue treatment after the administration of the first dose of trial medication will not be replaced. See Section 7.13 for replacement of subjects missing assessments due to COVID-19.

6.0 TRIAL TREATMENTS

6.1 Investigational medicinal product

MC2-25 cream 30 mg/g is a white oil-in-water, topical emulsion containing L-Alanyl-L-Glutamine in the aqueous phase at concentrations of 3% (w/w). In addition to the active ingredient, the formulation contains Triglycerides medium chain, Paraffin liquid, Glycerol, Carbomer interpolymer type A, Phenoxyethanol, Macrogol lauryl ether (4), Citric acid, Sodium Benzoate, Polysorbate (20), Sodium hydroxide, and Purified water.

6.2 Vehicle product

MC2-25vehicle is identical to the IMP except for the active ingredient.

6.3 Dosing regimen

MC2-25 cream or MC2-25 vehicle is to be applied twice daily, in the morning and evening, to areas with CKD-aP. The treatment must be applied in a thin even layer to affected areas and rubbed in gently to ensure that the treatment areas are saturated. Treatment of all areas with CKD-aP must be continued until the Week 12 (or EoT) visit. This is also applicable for areas becoming itch-free during trial participation and new areas of CKD-aP identified after the Baseline visit.

The daily dose should not exceed 50 g. Detailed application instructions will be provided in the subject instructions.

